#### 2.5.2.1 Progression-free Survival

No formal statistical tests will be performed for PFS. A Kaplan-Meier curve for PFS in each treatment arm will be displayed.

The difference between the two treatment arms will be estimated using the **hazard ratio** stratified by the stratification factors at randomization (exclude centre).

The analysis of PFS will also be presented for each level of each stratification factor and hazard ratio with corresponding 90% CI will be reported. An un-stratified Cox regression model with stratification factors as

covariates will be fitted. In all regression analyses, all patients with missing value in any covariate will be deleted from the analysis. (Table 10, 11, Figure 1)

For patients who developed PFS events, the type of progression events and summary of progression will be tabulated (Table 12).

#### 2.5.2.2 Overall Survival

The analyses of OS will be similar to these of PFS (table 13, 14, 15, Figure 2).

KM plots for survival curves and estimations of HRs with (90% CI) will be reported.

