### 1.2 Sample Size Determination

The objective of this trial was neither to test superiority nor to test noninferiority between two arms. The sample size is based on estimating the hazard ratio (HR) of two arms (experimental vs. control) within a 90% confidence interval (CI). For a 1:1 randomization with 1 year accrual and one-year additional follow-up. If we observe approximately 58 progression events in each arm, the upper bound of the 90% CI will be 1.36 times the estimated HR and the lower bound will be 0.74 times the estimated HR. Assuming a median PFS of approximately 10 months for both treatment arms, duration of accrual and follow-up both at 1 year, and a dropout rate of 10%, the study would need to enroll approximately 90 subjects in each arm.

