### 1.3 Timing of the Analyses

There will be no interim analysis for efficacy. An interim safety analysis was conducted in August, 2016, when 24 patients were enrolled and evaluable for toxicity. The final analysis will be conducted with a total of 116 PFS events observed. This is expected to happen two years after the trial activation.

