#### 2.5.2.3 Response Rate and Clinical Benefit Rate

Response rates (percentages of CR/PR as best response) will be reported by treated arms for patients evaluable for response.

Clinical benefit rates (percentages of CR/PR/SD as best response) will be reported by treated arms for patients evaluable for response.

Response rates and clinical benefit rates will be compared between two arms using the Cochran-Mantel-Haenszel test adjusting for stratification factors at randomization (Table 16).

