CTC AE 4.0 Hematology / Biochemistry table

Table 8. Baseline Non-Hematologic Adverse Event

CTC AE 4.0 Non-Hematologic Adverse Event table

Table 9. Baseline Concomitant Medication

All randomized patients	Palbociclib 100mg N = ***	Palbociclib 125mg N = ***	Total N = ***
Any baseline Concomitant Medication			
Yes	XX (XX)		
No	XX (XX)		

*Table 10. Log Rank and Cox Regression Model for PFS Survival*

Data set: All Randomized Patients				
	Univariate HR (95% CI)		Multivariate HR(95% CI) 	
Treatment (Arm 1 vs. Arm 2) (stratified)	***		--	
Treatment (Arm 1 vs. Arm 2) (un-stratified)				
ECOG PS (0 vs 1 or 2)				
Age (continuous)				
Histology (Ductal vs Labural)				
Grade				

(1) Based on Cox Model with all factors included.

*Table 11: PFS by Subsets*

Data set: All Randomized Patients			
	Number of patients (%)		
	Palbociclib 100mg N (# of events)	Palbociclib 125mg N (# of events)	HR (95% C.I.)
Visceral metastasis (at baseline)			
Yes	** (**)	** (**)	** (**)
No	** (**)	** (**)	** (**)
Duration of exposure to most recent endocrine therapy prior to randomization (at baseline)			
≥ 6 months (advance)	** (**)	** (**)	** (**)
< 6 months (advance)	** (**)	** (**)	** (**)
≥ 24 months (adjuvant)	** (**)	** (**)	** (**)
< 24 months (adjuvant)	** (**)	** (**)	** (**)
Planned use of endocrine therapy (at baseline)			
Fulvestrant	** (**)	** (**)	** (**)
Tamoxifen	** (**)	** (**)	** (**)
Aromatase Inhibitor	** (**)	** (**)	** (**)

*Table 12: PFS event Summary*

Data set: All randomized Patients		
	Number of Patients (%)	
	Palbociclib 100mg N = ***	Palbociclib 125mg N = ***
Patients with PFS event	*** (**)	*** (**)
Progression event	**	**
Death	**	**
Patients who were censored	*** (**)	*** (**)
Reason Censored		
No PFS event	**	**
Withdrawal of Consent	**	**

*Table 13. Log Rank and Cox Regression Model for Overall Survival*

Data set: All Randomized Patients				
	Univariate HR (95% CI)	Log-rank p-value	Multivariate HR(95% CI) 	Multivariate p-value
Same as PFS (table 10)	*** (*, *)	***	*** (*, *)	***
	*** (*, *)	***	*** (*, *)	***
	*** (*, *)	***	*** (*, *)	***
	*** (*, *)	***	*** (*, *)	***
	*** (*, *)	***	*** (*, *)	***
	*** (*, *)	***	*** (*, *)	***

(1) Based on Cox Model with all factors included.

*Table 15: Death Summary*

	Number of Patients (%)		
	Data set: All randomized Patients		
	Palbociclib 100mg N = ***	Palbociclib 125mg N = ***	Total N =
Patients who died			
Cause of Death			
Breast Cancer only			
Other primary malignancy			

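### In a trial framed as estimation, response and clinical benefit are compared between arms only by a CMH p-value, with no effect estimate or interval; the OS text and the Table 13 shell also differ on p-values

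*SAP*

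**What the plan says.** Section 1.1 makes estimation of the PFS hazard ratio the primary objective and lists response rate, clinical benefit rate and OS among the secondary ones. Section 1.2 adds that "The objective of this trial was neither to test superiority nor to test noninferiority between two arms" and bases the sample size on interval width: with about 58 events per arm, the plan expects that "the upper bound of the 90% CI will be 1.36 times the estimated HR and the lower bound will be 0.74 times the estimated HR". For the primary endpoint, section 2.5.2.1 says "No formal statistical tests will be performed for PFS".

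For response and clinical benefit, section 2.5.2.3 reports rates by arm and then says "Response rates and clinical benefit rates will be compared between two arms using the Cochran-Mantel-Haenszel test", adjusted for the stratification factors. The Table 16 shell has counts and percentages by arm, with footnotes for two CMH p-values. Neither place asks for a difference, an odds ratio or an interval.

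For OS, section 2.5.2.2 says "The analyses of OS will be similar to these of PFS" and names Kaplan-Meier plots and hazard ratios with 90% intervals. The Table 13 shell has hazard-ratio columns, but also a "Log-rank p-value" column and a p-value column for the multivariate model. As extracted, Table 10 (PFS) shows no p-value headings.

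Section 2.3 sets a general default: comparisons between arms use a two-sided 5% test unless something else is specified. It makes no multiplicity adjustment for the other clinical endpoints.

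**The concern.** A trial planned to estimate should say, for each endpoint on which it compares the arms, how large the difference is and how uncertain it is. For PFS and OS the SAP does so. For response and clinical benefit it replaces the estimate with a test result. A non-significant CMH p-value could then be taken as evidence that the two regimens respond alike, although the data may be compatible with a difference of ten points or more in either direction. A chance p-value below 0.05 would carry no statement of size.

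For OS the stake is smaller. A programmer working from section 2.5.2.2 would produce hazard ratios and intervals only; one working from Table 13 would add log-rank and Cox p-values. Which output appears should not depend on which part of the SAP is followed.

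**Working it through.** **1. The plan's own precision figure.** Inputs from section 1.2: 58 events per arm, 90% interval (z = 1.645).

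- SE(log HR) = sqrt(1/58 + 1/58) = 0.1857
- Factors = exp(±1.645 × 0.1857) = 1.357 and 0.737

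These match the stated 1.36 and 0.74, and 2 × 58 = 116 matches section 1.3 ("The final analysis will be conducted with a total of 116 PFS events observed"). The design rests on interval width; no power or test level enters it.

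**2. The same kind of figure for response and clinical benefit.** The SAP gives no response rate and no number evaluable. Assumed: 60 to 90 evaluable per arm (90 being the planned enrolment per arm), and the same rate p in both arms. Stratification is ignored for this rough size.

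Half-width of the 90% interval for the difference = 1.645 × sqrt(2p(1 − p)/n)

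| Rate p | n = 60 per arm | n = 90 per arm |
|---|---|---|
| 20% | 12.0 points | 9.8 points |
| 25% | 1.645 × sqrt(0.375/60) = 13.0 points | 1.645 × sqrt(0.375/90) = 10.6 points |
| 60% | 14.7 points | 12.0 points |

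The 60% row is an illustrative higher rate for clinical benefit, which also counts stable disease.

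**3. What the p-value alone would show.** For true rates of 25% and 35% (assumed), a two-sided 5% test of two proportions has power of about 22% with 60 per arm and 31% with 90 per arm. For 60 per arm:

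- pooled SE = sqrt(2 × 0.30 × 0.70/60) = 0.0837
- unpooled SE = sqrt((0.1875 + 0.2275)/60) = 0.0832
- z = (0.10 − 1.96 × 0.0837)/0.0832 = −0.77, so power = 0.22

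Under these assumptions non-significance is the likelier result even when the rates differ by ten points.

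**4. A 5% p-value beside a 90% interval.** The two can point different ways. With 60 per arm and a rate near 25%, the SE of the difference is about 0.079. Observed differences between about 13.0 points (1.645 SE) and 15.5 points (1.96 SE) would exclude zero from the 90% interval while p stays above 0.05. That is a reason to label the p-value descriptive.

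**5. OS, text against shell.**

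| Place | Hazard ratio with interval | p-value |
|---|---|---|
| Section 2.5.2.2 | yes | not mentioned |
| Table 13 | yes | log-rank and multivariate |
| Section 2.3 default | – | two-sided 5% test unless otherwise specified |

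The SAP gives no expected number of deaths. With 1:1 allocation, the 90% factors exp(±1.645 × 2/sqrt(d)) are 0.59 to 1.68 for an assumed d = 40, 0.65 to 1.53 for 60, and 0.69 to 1.44 for 80. This interval is already planned, so for OS the informative quantity is not missing.

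**The case against.** Much can be said for the SAP as written.

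- **OS tests are not forbidden.** The ban in section 2.5.2.1 covers PFS only, and the default in section 2.3 could permit an OS test. A reader might infer that Table 13 breaks an express rule. The text does not support that: it says similar, not identical.
- **The Table 13 stub is about rows.** The entry pointing back to Table 10 stands in the row-label column and replaces the list of covariates; it does not say that the columns match. The extracted Table 10 has blank header cells where Table 13 has its p-values, and both titles mention the log-rank test. Whether PFS headings were removed on purpose cannot be settled from the document.
- **The OS interval is planned.** A reader might infer that the OS p-values hide how large a survival difference remains possible. They do not, since the hazard ratio and its interval stand beside them.
- **The CMH test is permitted and consistent.** Section 2.5.2.3 and Table 16 agree with each other. Table 16 gives counts by arm, so anyone can compute a crude difference and interval.
- **Low power for secondary endpoints is normal in a phase II trial**, and the rates and numbers used above are assumed.

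All of this stands. It removes any claim of a direct contradiction and any demand that the CMH test be dropped. It does not supply what is missing: the crude difference that a reader could compute ignores the strata for which the planned comparison adjusts, and an estimate left to the reader is not a pre-specified one.

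**Conclusion.** The point holds in a limited form. For response and clinical benefit, a trial framed as estimation plans no between-arm estimate and no interval, only a stratified p-value. The uncertainty left unreported is about plus or minus 11 to 13 percentage points at a 25% rate with 60 to 90 evaluable patients per arm, and about 10 to 15 points over the wider range of rates in the table; these sizes rest on assumed rates and numbers.

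For OS, section 2.5.2.2 and Table 13 list different outputs and the SAP does not say whether OS is tested. That is an ambiguity to resolve; it hides no estimate.

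The stated precision of 1.36 and 0.74, the 116 events and the primary PFS analysis are unaffected.

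**What to change.** 1. In section 2.5.2.3 and Table 16, add for response rate and for clinical benefit rate the Mantel-Haenszel stratified risk difference or odds ratio with its 90% confidence interval, beside the CMH p-value. Choose one measure and name it in advance. Label the p-value descriptive.
2. Reconcile section 2.5.2.2 with Table 13: either delete the two p-value columns so that the shell matches the text, or state in section 2.5.2.2 that the OS p-values are descriptive.

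The cost is a sentence or two of SAP wording and a few cells in the shells. The data and strata are those already used for the CMH test. The only downside is less emphasis on secondary p-values.

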#### 2.5.2.3 Response Rate and Clinical Benefit Rate

Response rates (percentages of CR/PR as best response) will be reported by treated arms for patients evaluable for response.

Clinical benefit rates (percentages of CR/PR/SD as best response) will be reported by treated arms for patients evaluable for response.

Response rates and clinical benefit rates will be compared between two arms using the Cochran-Mantel-Haenszel test adjusting for stratification factors at randomization (Table 16).

#### 2.5.2.4 Duration of Response

Duration of response (median, Q1, Q3, min, max) will be reported by treated arms for patients with CR/PR. The difference in duration of response between the two treatment arms will be tested using the log-rank test adjusting for stratification factors at randomization (Table 17).

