## 2.3 Analysis Conventions

All comparisons between treatment arms will be carried out using a two-sided test at an alpha level of 5% unless otherwise specified. No formal adjustments will be made for the multiplicity of inferences for the other clinical endpoints.

Baseline stratification factors (excluding centre) that will be used to adjust the analyses where appropriate are listed below:

- Visceral metastases (yes versus no)
- duration of exposure to most recent endocrine therapy prior to randomization (4 groups)
  - duration  $\geq$  6 months versus  $<$  6 months in the advanced/metastatic setting
  - duration  $\geq$  24 months versus  $<$  24 months in the adjuvant setting
- Planned use of Fulvestrant versus Tamoxifen versus Aromatase Inhibitor (AI)

\*Add missing/unknown category whenever appropriate.

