#### 2.5.1.4 Response Duration

For patients with documented CR or PR, duration of response is calculated from the time of CR or PR (whichever is first recorded) until the first date that recurrent or progressive disease is objectively documented or death occurs. If a patient has not progressed or died at the time of the final analysis, duration of response will be censored on the date of the last disease assessment.

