Other condition or circumstance			
Patients who were censored			
Reason Censored			
Still Alive			
Withdrawal of Consent			

*Table 16: Response to Treatment*

	Number of Patients (%)		
	Data set: All treated patients with measurable disease		
	Palbociclib 100mg N = ***	Palbociclib 125mg N = ***	
Response to treatment			
CR	XX (%)	XX (%)	XX (%)
PR			
SD			
PD			

\*Stratification CMH test p-value for response rate:  $(CR+PR)/(CR+PR+SD+PD)$

\*\*Stratification CMH test p-value for clinical benefit rate:  $(CR+PR+SD)/(CR+PR+SD+PD)$

*Table 17: Duration of Response*

	Number of Patients (%)		
	Data set: All patients with CR/PR		
	Palbociclib 100mg N = ***	Palbociclib 125mg N = ***	Stratified p-value from log rank test
Duration of response			
Median	XX	XX	p-value =
Min	XX	XX	-
Max	XX	XX	-
Q1	XX	XX	-
Q3	XX	XX	-

*Table 18: Dose information*

Data set: All treated Patients: Cumulative dose (mg)			
	Number of patients		
	Palbociclib 100mg N = ***	Palbociclib 125mg N = ***	Total N = ***
Median	***	***	***
Min	**	**	**
Max	**	**	**
Q1			
Q3			

Cumulative dose (mg)

n

Mean

Std

Median

Min

Max

Q1

Q3

*Similar tables for*

*Daily dose(mg),*

*Dose intensity (mg/week)*

*Relative dose intensity (percent)*

*Cycle 1 and 2 dose intensity (mg/week)*

*Cycle 1 and 2 relative dose intensity (percent)*

90% or more dose intensity: N and percent

Data set: All treated Patients			
90% or more dose intensity: N and percent	Number of patients		
	Palbociclib 100mg N = ***	Palbociclib 125mg N = ***	Total N = ***
No	***	***	***
Yes	**	**	**

Cycle 1 and 2 90% or more dose intensity: N and percent

Data set: All treated Patients			
Cycle 1 and 2 90% or more dose intensity: N and percent	Number of patients		
	Palbociclib 100mg N = ***	Palbociclib 125mg N = ***	Total N = ***
No	***	***	***
Yes	**	**	**

*Table 19: Dose modifications*

Data set: All treated Patients			
At least one dose modification	Number of patients		
	Palbociclib 100mg N = ***	Palbociclib 125mg N = ***	Total N = ***
Yes	**	**	**
Reason of dose modifications Reason 1 Reason 2 ...			

Data set: All treated Patients			
At least done dose Reduction	Number of patients		
	Palbociclib 100mg N = ***	Palbociclib 125mg N = ***	Total N = ***
Yes	**	**	**
Reason of dose reduction Reason 1 Reason 2 ...			

Data set: All treated Patients			
Patients with dose discontinuation	Number of patients		
	Palbociclib 100mg N = ***	Palbociclib 125mg N = ***	Total N = ***
Yes	**	**	**
Reason of dose discontinuation			

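### Duration of response is tested between arms among responders only, a group formed after randomization, so the p-value is not a randomized comparison and can favour the arm with fewer responders

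*SAP*

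**What the plan says.** SAP section 2.5.1.4 starts the clock at the first response: "For patients with documented CR or PR, duration of response is calculated from the time of CR or PR (whichever is first recorded"). Durations without progression or death are censored at the last disease assessment.

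Section 2.5.2.4 sets the population, "Duration of response (median, Q1, Q3, min, max) will be reported by treated arms for patients with CR/PR", and then the comparison: "The difference in duration of response between the two treatment arms will be tested using the log-rank test", with adjustment for the randomization strata. The shell for Table 17 agrees. Its data set is "Data set: All patients with CR/PR" and its last column is "Stratified p-value from log rank test".

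Section 2.3 supplies the error rate: "All comparisons between treatment arms will be carried out using a two-sided test at an alpha level of 5% unless otherwise specified". It makes no multiplicity adjustment for the other clinical endpoints. Nothing calls the duration test descriptive or exploratory; section 2.9.2 uses the word exploratory for quality of life only.

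For the primary endpoint, section 2.5.2.1 says: "No formal statistical tests will be performed for PFS".

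**The concern.** Randomization makes the two arms comparable as wholes. It does not make the responders in one arm comparable with the responders in the other, because who responds depends on the schedule received. If one schedule brings in additional patients who would not have responded on the other, and their responses are shorter than average, the duration curve of that arm falls although no patient is worse off. A log-rank test on responders reads that fall as a disadvantage. The stratification factors are measured before randomization, so adjusting for them does not remove selection that happens afterwards.

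At stake is the reading of the schedule comparison. A small p-value in Table 17 could be taken as evidence against the schedule that helped more patients. A large one says little, because few responders are expected.

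**Working it through.** **The plan's own precision figure, for reference.** Section 1.2 assumes 58 PFS events per arm and a 90% CI. The factor is exp(±1.645 × √(1/58 + 1/58)) = 1.36 and 0.74, as the SAP states. The SAP gives no figure for duration of response.

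**Worked example (assumed inputs).** Arm A has 18 responders with exponential durations, median 10 months. Arm B has 18 responders of the same kind plus 9 extra responders with median 4 months.

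- Responders: 27 against 18, so 50% more in arm B.
- Median in arm B: solve (2/3)·exp(−ln2·t/10) + (1/3)·exp(−ln2·t/4) = 0.5. At t = 7.2 the terms are 0.405 + 0.096 = 0.50, so the median is 7.2 months against 10 in arm A.
- Hazard ratio, B against A, with censoring uniform over 6 to 18 months: about 1.35 in large samples; 1.41 in a simulation of the example.
- Total expected time in response, uncensored: arm A 18 × 10/ln2 = 260 months; arm B 260 + 9 × 4/ln2 = 312 months. The arm that looks worse on duration delivers more time in response.
- Unstratified log-rank test, two-sided 5%, about 28 events per simulated trial: significant in favour of arm A in about 10% of trials. The nominal rate in that direction is 2.5%.

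**Range of assumptions.** There are 81 evaluable patients per arm (90 less 10%). Patients who would respond on either schedule have median duration 12 months in both arms. One arm adds extra responders. Censoring is uniform over 8 to 20 months, with 4,000 simulated trials per row.

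| Response rates | Median duration of extra responses | Significant in favour of the arm with fewer responders |
|---|---|---|
| 20% vs 30% | 6 months | 7.1% |
| 20% vs 30% | 4 months | 11.8% |
| 20% vs 35% | 4 months | 19.0% |
| 25% vs 40% | 4 months | 18.4% |
| 30% vs 50% | 4 months | 23.3% |
| 25% vs 25% | no extra responders | 2.8% |
| Unequal rates as above | 12 months | 2.4% to 2.6% |

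In the first five rows the test favours the arm with more responders in under 1% of trials. The last two rows are the control: with the same kind of responder in both arms, the error rate is close to nominal. The distortion comes from the difference in responder mix.

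Mean time in response per patient, with non-responders counted as zero and no censoring, at 20% vs 35%:

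- Fewer responders: 0.20 × 12/ln2 = 3.5 months.
- More responders: 3.5 + 0.15 × 4/ln2 = 4.3 months.

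**Information available.** The 90% CI factor with d duration events split equally is exp(1.645 × 2/√d):

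- d = 24: 1.96.
- d = 40: 1.68.

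With 162 evaluable patients, 15% to 35% responding (24 to 57 patients) and 70% of those with an event, d is 17 to 40. Power for a hazard ratio of 0.6 is Φ(√d/2 × |ln 0.6| − 1.96) = 18% to 36%. The factors in section 2.3 form 2 × 4 × 3 = 24 strata. A few dozen responders spread over these would leave many strata without patients from both arms, which weakens a stratified test further.

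**The case against.** The strongest reply concerns weight. Duration of response is one of several secondary endpoints, and no success criterion or sample size depends on it. Table 16 shows response rates by arm, so a reader can see how many responders stand behind each duration, and Table 17 labels its data set openly. PFS and OS are compared in all randomized patients. The SAP also tests other secondary outcomes (response rate, clinical benefit rate, quality of life), so a test here does not contradict leaving PFS untested. Section 2.1 gives response analyses their own population, so there is no clear breach of the intention-to-treat rule either.

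The size is also hypothetical. Nothing in the SAP suggests that one schedule would add short responses, and the error rate is nominal when responder mix is equal. Even in the worked example the test is usually not significant. With responders spread at random over 24 strata, the misleading rate falls to about 7%.

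Most of this stands and limits the weight of the point. It does not defend the test. Showing response rates in another table does not turn the p-value into a randomized comparison, and 7% is still nearly three times the nominal 2.5%. The contrast with PFS shows poor fit with an estimation design; the case does not depend on it.

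**Conclusion.** The concern holds. The SAP plans a two-sided 5% log-rank test on a group defined by an outcome after randomization, does not label it descriptive, and adjusts only for baseline factors. The test can favour the arm with fewer responders: in about 7% to 23% of simulated trials against a nominal 2.5%, when the other arm gains shorter responses. These rates rest on assumed response rates, durations and censoring, and they return to nominal if responders are alike in both arms. Direction and size in this trial cannot be known from the SAP.

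Reporting duration among responders is standard and is not at fault; the formal between-arm test is. The point is of moderate weight and should be changed. It leaves the PFS estimate and the sample size untouched.

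**What to change.** In section 2.5.2.4, delete the sentence that plans the log-rank test. In Table 17, delete the p-value column. Replace them with Kaplan-Meier median and quartiles by arm with 90% CI, stated to be descriptive. Naming Kaplan-Meier also closes a small gap: section 2.5.1.4 censors durations, but section 2.5.2.4 does not name a method that allows for censoring.

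A comparison between arms is optional. If one is wanted, base it on all randomized patients, for example mean time in response up to a fixed time with non-responders counted as zero. That is a new quantity, and its truncation time would have to be fixed before the data are examined.

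The core change is one sentence and one table column, with no new data. The cost is that this secondary endpoint carries no p-value.
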